6.7 Technical Feasibility Assessment of Edwards Cardioband System Implantation by **Sponsor**

The Sponsor will review applicable patient data collected at Screening and Baseline Visits (e.g. cardiac CT) to determine the technical feasibility of implanting the Edwards Cardioband System. The Sponsor may also assist the site in determining the most appropriate implant size for the patient.

Central Screening Committee Determination

After the Central Screening Committee (CSC) has reviewed all screening and baseline assessments and reached a decision on eligibility, the decision will be communicated to the site. The site will proceed to scheduling the case for approved patients in accordance with institutional procedures.

^{*}If TTE is more than 60 days from the procedure, a repeat TTE will be required.

Randomization Procedure 7

Patients will be prospectively randomized into the clinical study. Randomization will occur only after the patient provides informed consent, completes all required screening and baseline procedures, and satisfies the study eligibility criteria (including eligibility determination by the Central Screening Committee). Randomization shall be performed after cases have received final approval from the CSC and Sponsor and the case has been scheduled at the institution.

Eligible patients will be randomly assigned in a two to one (2:1) ratio to either treatment with Edwards Cardioband System + Guideline Directed Medical Therapy (Device Group) versus Guideline Directed Medical Therapy alone (Control Group).

Randomization assignment will be generated via the randomization module of the EDC system. Randomization scheme will be based on random blocks and will be stratified by:

- study center
- baseline ischemic vs. non-ischemic disease

This randomization schedule (list) will be masked to study patients, site personnel, study team and Sponsor. Only the un-blinded statistician and designates will be privy to the masked randomization scheme.

A patient is not considered randomized until the randomization assignment has been dispensed. If at any time after randomization a patient becomes ineligible or withdraws, the patient is still considered randomized.

8 TREATMENT (EDWARDS CARDIOBAND SYSTEM INDEX PROCEDURE / GDMT)

8.1 Prior to Index Procedure (for patients assigned to Device group only; timing per local institutional standard of care)

Note: The goal is to conduct the Edwards Cardioband System index procedure within 7 days of the date of randomization. Randomization should occur as close as possible prior to the scheduled procedure to minimize the amount of time between randomization and procedure.

The following data must be collected prior to the index procedure, according to the local institutional standard of care.

Pregnancy Test (for females of child bearing potential)

PROTOCOL NUMBER: 2017-05

- 7-05
- Complete Blood Count
- Coagulation Panel
- Chemistry Panel
- Cardiac Biomarkers (troponins or CK/CK-MB)
- Adverse Events

8.2 Edwards Cardioband System Index Procedure (for patients assigned to Device group only)

The following data must be collected during the index procedure:

- Transesophageal Echo (TEE)
- Procedural details
- Adverse Event Assessment
- Anticoagulation/ antiplatelet therapy administered intra-procedure.

Note: If, during the assessment of the patient at any time between the randomization and the time of the procedure, it is determined that the patient is no longer eligible for the study, the patient shall be withdrawn and will not be counted towards the pre-planned sample size (i.e. the enrollment will continue until the pre-planned 375 non-screen-failures are enrolled). A patient who is determined to be a screen-failure on the day of procedure and received diagnostic procedures in the procedure room, shall be followed for 30 days for the purposes of safety.

The mitral valve reduction procedure will be performed in a transcatheter manner to deliver and deploy the Edwards Cardioband System. The Edwards Cardioband System procedure may be performed in a standard operating room, hybrid operating room, or cardiac catheterization lab. In any of these settings emergency equipment and resources including adequate blood products, external defibrillator paddles, proper anesthesia administration, and monitoring capabilities must be available. The team performing the Edwards Cardioband System procedure will include an anesthesiologist, an interventional cardiologist or surgeon experienced in transceptal and transcatheter valve procedures, and an echocardiographer as per local standard of care.

Note: A recommended technique is presented in the following sections. It is recognized that individual patient anatomic variation or surgical/interventional conditions may necessitate modifications to the outlined procedures. However, to the extent possible, physicians should adhere to the procedure steps

8.2.1 Antithrombotic Therapy

To protect patients from bleeding or thromboembolic events, a recommended process for antithrombotic therapy is provided below. Investigators may utilize their institutional procedures for anticoagulation/ antiplatelet therapy, in recognition of various agents available as well as individual patient factors such as CHA₂DS₂-VASC score.

8.2.1.1 During Index Procedure

 IV unfractionated heparin with a target ACT ≥ 250 seconds or bivalirudin (no ACT monitoring necessary)

8.2.1.2 Post-Index Procedure

- Aspirin (ASA) 75 100 mg daily by mouth, indefinitely
- Clopidogrel 75 mg daily by mouth, for 6 months
- If oral anticoagulation is indicated, no clopidogrel is necessary unless indicated for post-PCI indication. If anticoagulation is given along with clopidogrel (for example due to a PCI history and indication) ASA may be discontinued at investigator's discretion.

To monitor anticoagulation for patients on vitamin-K antagonists, International Normalized Ratio (INR) should be measured at each follow up visit. Additional INR testing may be performed according to institutional practice or the physician's discretion.

8.2.2 Antibiotic Prophylaxis

It is recommended that all patients undergoing device implant be prophylactically treated for endocarditis per AHA recommendations.²⁶

8.2.3 Patient Preparation in Procedure Room

Prior to draping, place the booster plate associated with the Edwards Cardioband System under the patient's leg in the region of the knee, and adjust booster apparatus per IFU.

The patient is prepped and draped for a standard transseptal procedure.

Non-sterile, external defibrillator pads are placed behind the right shoulder and on the left flank, away from femoral insertion sites. Alternatively, if sterile external defibrillator pads are available, one can be placed over the sternum and one directly posterior on the back.

General anesthesia or conscious sedation is induced and the patient ventilated according to patient's hemodynamic condition and institutional practices. Due to the duration of the

procedure an anesthesiologist should administer sedation/anesthesia. General anesthesia is encouraged to facilitate use of transesophageal echocardiography.

8.2.4 Implantation Procedure

Note: Prior to preparation and loading of the Edwards Cardioband System, the serial number of the implant should be recorded on the supplied Patient Implant Card. Similarly, the serial number of the implant should be recorded in hospital records.

The major steps for Edwards Cardioband System utilization are outlined below. Refer to the Instructions for Use (IFU) for complete details on device preparation and use:

1.	
	1

8.2.5 Edwards Cardioband System/MR Assessment

After implantation of the Edwards Cardioband System, transesophageal echocardiography should be performed per the Echocardiography Core Lab study manual to assess mitral regurgitation after performing device reduction.

8.2.6 Index Procedure Completion and Tissue Closure

Once all maneuvers are complete, catheters and sheaths are withdrawn. The end of the procedure is defined as the time that the final catheter or sheath is withdrawn from the vasculature (does not include intravenous or other indwelling catheters used for medication delivery or patient monitoring). Catheter insertion site hemostasis and dressings should be performed according to institutional techniques.

8.2.7 Index Procedure through Discharge

The patient should arrive wearing the activity monitor wrist watch at time of the index procedure hospitalization period. The patient will be asked to wear the activity monitor wrist watch through the hospitalization and allowed to remove the device during tests, evaluations, the index procedure, and as required by the treating physician. At index hospitalization discharge the patient should be wearing the activity monitor.

The following assessments will be recorded prior to, or at time of discharge (or at 30 days post index procedure, whichever comes first).

- Cardiovascular medications
- 12-lead ECG
- Transthoracic Echocardiography
- Cardiac Biomarkers (troponins or CK/CK-MB) [pre-intervention and post-index procedure: approximately 12-24 hours, 36-48 hours, 72 hours or at discharge if earlier. Thereafter, if cardiac biomarkers remain elevated, collect daily until values show a decline or patient is discharged.]
- Neurological Assessments:

Neurological Assessment will be conducted by a neurologist, a neurology fellow, or designee. Every effort should be made to have a neurologist or neurology fellow perform the neurological assessments, or alternatively, a trained research team member certified in stroke assessment, which consist of:

NIHSS

Modified Rankin Scale (mRS): mRS can be obtained by a certified research team member via phone interview with the patient or caregiver member if the patient is unable to visit the research office.

Adverse Events

For purposes of this study, hospital discharge is defined as the date of discharge, or 30 days following the post-index procedure if patient remains in hospital, whichever occurs first.

Guideline Directed Medical Therapy (for both Device and Control groups) 8.3

Patients with a documented intolerance to Guideline Directed Medical Therapy (GDMT) will be eligible for study inclusion. All patients (i.e. whether assigned to Device and Control groups) shall continue to receive stable Guideline Directed Medical Therapy as directed by current heart failure guidelines (including use of cardiac resynchronization therapy, as indicated).^{27,28} This implies that the GDMT regimen in principle remains unchanged until primary efficacy endpoint, unless medically warranted. Changes to GDMT (doubling or halving of dose) will be documented including whether these occurred due to improvement, deterioration, or no change in the patient's condition. Medical management should continue under the direction of a heart failure specialist at regular intervals according to current heart failure guidelines.^{27,28}

FOLLOW-UP EVALUATIONS

Follow-up evaluations will be scheduled for 30 days, 180 days, 1 year, 2 years, 3 years, 4 years, and 5 years.

- For patients assigned to the Device group, the follow-up visits are scheduled based on the date of the Edwards Cardioband System index procedure.
- For patients assigned to the Control group, the follow-up visits are scheduled based on the date of randomization.
- Note: A patient in the Control group may be offered an opportunity to receive an Edwards Cardioband System after they have been followed for a minimum of 1 year and completed their primary efficacy endpoint assessment. At the time of their 1 year follow-up visit, if the patient chooses to receive the investigational device, they will be evaluated in accordance with the eligibility criteria (including concurrence by the site Heart Team and the CSC). If the patient is still eligible for enrollment, he/she will be offered an opportunity to receive the device. If the patient receives the Edwards Cardioband System implant, he/she shall be followed in accordance with the clinical

protocol schedule or at a minimum for two years if the product has received PMA Approval. This group shall be summarized as a separate cohort.

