5.2 Primary Safety Endpoint (Evaluated through 30 Days post procedure) [Device Group only]

Overall rate of device and procedure related Major Adverse Events (MAEs) through 30 days post-procedure (including death, stroke, myocardial infarction, pericardial effusion requiring drainage, left circumflex coronary artery injury requiring intervention, mitral valve reintervention and access site and vascular complications requiring intervention. The primary safety endpoint was chosen to detect any concerns relating to safety of the Edwards Cardioband System implantation procedure.

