13.4.3 Analysis of the Safety Endpoints

The overall rates of device and procedure related Major Adverse Events (MAEs) through 30 days post procedure, (primary safety endpoint) as well as the components and secondary safety endpoints, will be calculated, with 95% confidence intervals.

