Defined as admission to inpatient unit or ward in the hospital for ≥ 24 hours, including emergency department stay. Hospitalizations planned for pre-existing conditions are excluded unless there is worsening of baseline condition.

HEART FAILURE HOSPITALIZATION

Both of the following additional criteria are present:

- Symptoms, signs and/or laboratory evidence of worsening heart failure
- Administration of intravenous or mechanical heart failure therapies

Patients hospitalized with heart failure are further sub-classified as:

- Primary heart failure hospitalization, including heart failure secondary to other cardiac related hospitalization such as for myocardial infarction.
- Secondary heart failure hospitalization heart failure has occurred during an otherwise non-cardiac related hospitalization.

OTHER CARDIOVASCULAR HOSPITALIZATION

Including hospitalizations such as for coronary artery disease, acute myocardial infarction, hypertension, cardiac arrhythmias, cardiomegaly, pericardial effusion, atherosclerosis, stroke, or peripheral vascular disease without qualifying heart failure.

NON-CARDIOVASCULAR HOSPITALIZATION

Hospitalizations that are not due to heart failure or other cardiovascular hospitalizations, as defined above.

LEFT CIRCUMFLEX ARTERY INJURY REQUIRING INTERVENTION

Injury to the left circumflex (LCX) artery which requires intervention may include occlusion, perforation, laceration, dissection, ligation, suture or anchor misplacement. Other potential causes may include a thrombus or hematoma formation due to surgical trauma. Vasospasm of the LCX artery is excluded in this definition unless it requires percutaneous intervention.

PROTOCOL NUMBER: 2017-05

MITRAL VALVE STENOSIS

Defined as a mitral valve orifice area of less than 1.5 cm² as measured by the

Echocardiography Core Laboratory.

MYOCARDIAL INFARCTION

Myocardial infarction (MI) classification and criteria for diagnosis is defined as follows:³¹

1. Peri-procedural MI (≤ 48 hours after Edwards Cardioband System procedure)

1.1. In patients with normal baseline CK-MB (or cTn):

Peak Creatinine Kinase myocardial b fraction (CK-MB) measured within 48

hours of Edwards Cardioband System implantation rises to ≥10x of the local

laboratory upper limit of normal (ULN) plus new ST-segment elevation or

depression of ≥1 mm in ≥ 2 contiguous leads (measured 80 ms after the J-

point) or to ≥5x ULN with new pathological Q waves in ≥2 contiguous leads or

new persistent LBBB.

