1.2. In patients with elevated baseline CK-CB (or cTn):

The CK-MB (or cTn) rises by an absolute increment equal to those levels

recommended above from the most recent pre-procedure level plus new ECG

changes as described above.

1.3. In patients without CK-MB measurements and a normal baseline cTn,

A Cardiac Troponin (cTn (I or T)) level measured within 48 h of the PCI rises to

≥70x the local laboratory ULN *plus* new ST-segment elevation or depression

of \geq 1 mm in \geq 2 contiguous leads (measured 80 ms after the J-point) OR \geq 35x

ULN with new pathological Q waves in ≥ 2 contiguous leads or new persistent

LBBB.

2. Spontaneous MI (> 48 hours after Edwards Cardioband System procedure)

Page **102** of **113**

PROTOCOL NUMBER: 2017-05

Detection of rise and/or fall of cardiac biomarkers (preferably cTn) with at least one value

above the 99th percentile of the upper reference limit (URL) or ULN in the absence of

URL, together with at least one of the following:

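### Peri-procedural MI needs a new ECG change as well as an enzyme rise, but only the enzymes are timed to the 48-hour window, so a transient ST change can go unrecorded under full compliance

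*Protocol*

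**What the plan says.** **Endpoint.** Protocol Section 5.2 makes MI part of the primary safety endpoint: "Overall rate of device and procedure related Major Adverse Events (MAEs) through 30 days post-procedure (including death, stroke, myocardial infarction". MI is also a secondary safety endpoint in Section 5.3. Both are for the Device group only. Under Section 13.4.3 the rates "will be calculated, with 95% confidence intervals", and SAP Section 8.3 says the same. Neither document states a performance goal, hypothesis or power for safety.

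**Definition.** Appendix B, item 1, is headed "Peri-procedural MI (≤ 48 hours after Edwards Cardioband System procedure". Its three routes are:
- **1.1, normal baseline:** CK-MB at or above 10 times the "laboratory upper limit of normal (ULN) plus new ST-segment elevation or" depression, or the lower enzyme level with other findings: "point) or to ≥5x ULN with new pathological Q waves in ≥2 contiguous leads or" new persistent LBBB.
- **1.2, raised baseline:** an absolute increment equal to the levels "recommended above from the most recent pre-procedure level plus new ECG" changes.
- **1.3, troponin only:** at least 70 times ULN with ST change, or at least 35 times ULN with new Q waves or new persistent LBBB.

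**Schedule.** Section 8.2.7 times the biomarkers: "pre-intervention and post-index procedure: approximately 12-24 hours, 36-48 hours, 72 hours or at discharge if earlier". The 12-lead ECG stands in the same list without a time of its own, so only the lead-in to the list applies: "The following assessments will be recorded prior to, or at time of discharge (or at 30 days post index procedure, whichever comes first". The lists in Section 8.1 (before the procedure) and Section 8.2 (during it) contain no ECG. Tables 1 and 4 agree, and their later ECGs are at 30 days, 180 days and 1 year.

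**The concern.** The definition has two parts, and the schedule secures only one of them inside the window. No enzyme level is an MI by itself in the first 48 hours, so the classification depends on a tracing that may be taken after the ST change has resolved.

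Missed cases push the rate one way, toward a more favourable safety result. The rate is Device-only, so no control arm would reveal under-detection, and a confidence interval around an under-ascertained rate does not reflect it. The extent would also vary with each site's ECG habits. The implant is fixed along the posterior annulus (Section 1.2), and circumflex occlusion and perforation are listed as anticipated events (Appendix A, Table 7), so infarction around the procedure is a foreseeable event here.

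**Working it through.** The documents give no MI rate, major adverse event rate or length of stay, so there is no figure to reproduce. The check is whether the schedule supplies what the definition needs.

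| Needed for peri-procedural MI | Scheduled within 48 h | Source |
|---|---|---|
| Baseline enzyme | Yes, pre-intervention | 8.1, 8.2.7 |
| Post-procedure enzyme | Yes, 2 draws (about 12-24 h and 36-48 h), or at discharge if earlier | 8.2.7 |
| Baseline ECG | Screening tracing only | 6.6, Tables 1 and 4 |
| Post-procedure ECG | None required unless discharge falls within 48 h | 8.2.7, Tables 1 and 4 |

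The next scheduled ECG after the in-hospital one is at 30 ± 7 days, that is day 23 to day 37.

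Four compliant cases show where the gap lies:

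1. **Discharged within 48 hours.** The pre-discharge ECG falls inside the window. It may still miss a brief ST change, but a tracing exists.
2. **Stays longer; new Q waves or persistent LBBB.** A later in-hospital or 30-day tracing can show these, and the lower enzyme levels then suffice (5 times ULN for CK-MB, 35 times for troponin). Routes 1.1 and 1.3 attach the 48-hour limit to the enzyme measurement and write no deadline for the tracing.
3. **Stays longer; ST change persists.** A later in-hospital tracing can show it.
4. **Stays longer; ST change resolves, with no Q waves or LBBB.** Enzymes reach the upper level (CK-MB 10 times ULN, troponin 70 times, or the equivalent increment in 1.2). If the only in-hospital ECG follows resolution, the second part of the definition is never documented. The spontaneous-MI route, which accepts symptoms or imaging in place of an ECG, applies only after 48 hours, so it does not cover this event.

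Case 4 is the gap. With no symptoms to prompt an ECG, Section 11.4 adds to it. That section exempts laboratory variances judged not clinically significant from reporting, and Section 14.2 has the CEC review reported events. An enzyme rise that a site judged exempt might therefore not reach the CEC.

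**The case against.** The strongest reply is that the schedule is a minimum and several routes remain open. Much of that stands, and it rules out stronger readings that a reader might infer:

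- **That the pre-discharge tracing is the only post-procedure ECG.** It is the only scheduled in-hospital one. Sections 9.1 to 9.3 list a 12-lead ECG at 30 days, 180 days and 1 year.
- **That a patient without a tracing by 48 hours cannot meet the definition.** Cases 2 and 3 show otherwise.
- **That the whole MI component is exposed.** Spontaneous MI, MI with sudden death and pathological MI are separate routes and are unaffected.
- **That the ECG is typically very late.** Day 30 is a cap. The biomarker wording itself allows for discharge before 72 hours.
- **That a number of missed events can be given.** This would need an assumed MI rate and an assumed share of patients with an ECG in the window. Neither is in the documents, and counting every patient without such an ECG as missed would ignore the later-tracing routes.

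Clinically driven ECGs are not excluded. Section 11.4 exempts chest pain only when enzymes and ECG are unchanged, which presupposes that tracings are taken. Circumflex injury that needs intervention is already a separate component of the composite. Appendix B gives the CEC Charter precedence over the protocol on definitions, and the Charter is not among the documents.

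The gap survives these points. Nothing requires an unscheduled tracing in a patient without symptoms. An infarct from a circumflex injury that receives no intervention enters through the MI component, if at all. No Charter wording can supply an ECG that was not recorded.

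**Conclusion.** The mismatch is real and narrow. Under full compliance, a qualifying enzyme rise with a transient ST change in the first 48 hours can go unclassified. That can bias the peri-procedural MI count, and hence the Device-only primary safety rate, downward.

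The size cannot be derived from the documents. It depends on the peri-procedural MI rate, length of stay, how often ST change resolves without Q waves or LBBB, and how often sites record unscheduled ECGs. No stated pass/fail result turns on it, because safety is reported as a rate with an interval. It should still be corrected: the rate is to support a PMA application, and a tracing not taken in time cannot be recovered. The conclusion assumes that the protocol schedule is the operative one and that no unseen manual requires an earlier ECG.

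**What to change.** Reconcile Section 8.2.7 and Tables 1 and 4 with Appendix B. Time the already scheduled in-hospital 12-lead ECG to one of the existing biomarker draws within 48 hours, or at discharge if earlier. State that this tracing, any clinically driven tracing and the 30-day tracing go to the CEC with the enzyme values.

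The cost is a line in the schedule and in the CEC submission instructions. It adds no procedure, because an existing ECG is re-timed to an hour when blood is already drawn. Repeat tracings triggered by enzyme level would be extra procedures and are not part of this change.

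There are two drawbacks. A single earlier tracing can still miss some transient ST change. It also gives less late in-hospital evidence that an LBBB is persistent, although the 30-day ECG remains for that. The change helps only patients treated after it takes effect.

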3.1 Hypothesis

Transcatheter mitral valve repair with the Edwards Cardioband System, combined with guideline directed medical therapy (GDMT), will reduce mitral regurgitation (MR) and improve

MR symptoms and functional capacity in patients with functional MR as compared with GDMT alone.

STUDY DESIGN

This is a prospective, randomized, multicenter clinical evaluation of the Edwards Cardioband System for the treatment of clinically significant functional mitral regurgitation in MR patients who are treated in accordance with current ACC/AHA valve guidelines. 10,11

This investigational plan incorporates a roll-in cohort to provide experience in the use of the Edwards Cardioband System prior to randomizing patients into the pivotal study cohort at a given investigational site. The roll-in cohort will include a maximum of three patients per site (e.g. if 75 sites used, a maximum of 225 roll-in patients). Data for the roll-in patients will be presented and analyzed as a separate cohort. In the event that a roll-in procedure needs to be prematurely terminated prior to full placement of the system, the treating physician may opt to re-attempt the Edwards Cardioband procedure at a later time (typically after 30 days) for this roll-in patient. In such instances, screening and baseline assessments will be repeated as necessary to ensure that they fit within the prescribed timeframes.

This trial randomizes up to 375 eligible patients at up to 75 sites in North America and Europe on a 2:1 randomization ratio to the Edwards Cardioband System + GDMT (Device group) or to GDMT alone (Control group). Primary endpoint data will be available at 30 days (safety) and 1 year (efficacy), and long-term follow-up through 5 years is planned for all patients.

Therefore, it is expected that a maximum of 600 patients will be enrolled (up to 375 pivotal patients plus up to 225 roll-in patients).

A flow chart of the study (Figure 4) is provided on the following page to illustrate the overall design of the trial. Upon confirmation of patient eligibility, confirmatory testing shall be performed and a technical review of the case is performed by the Edwards Clinical support team to assist with device sizing and case planning with the operator(s). The study will utilize a Central Screening Committee (CSC) to evaluate each patient prior to enrollment. Patients shall then be scheduled for the procedure.

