Randomization is ideally performed within seven days prior to the scheduled procedure, but no more than 14 days prior. If a patient is randomized to control, the scheduled interventional case is cancelled and the patient is notified that they have been enrolled in the control/medical therapy arm of the trial and will not need to undergo an interventional procedure. The process of randomizing after a case is scheduled has been implemented to ensure that the time frame between randomization and actual treatment is minimized. As depicted in the flowchart, all

patients are followed for 30 days, 6 months, 1 year and annually for a total of 5 years post-index procedure or randomization in the case of the control population.

[figure not shown]

Figure 4: Clinical Study Design Flowchart

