12.2 Data Collection & Follow-Up for Discontinued/Withdrawn Patients

All randomized patients are considered eligible for the assigned treatment and protocol defined follow-up and will be required to adhere to the assessment schedule outlined in Table 4. Patients may withdraw at any time from the clinical study without jeopardy or prejudice. If a patient terminates from the study, the reason for study termination will be recorded. If termination is a result of an adverse event or death, an Adverse Event eCRF will also be completed. Patients who withdraw consent after treatment will not be required to undergo follow-up after withdrawal, but will still be considered part of the patient cohort.

Every attempt will be made to conduct an exit/final visit prior to a patient terminating from the study. The reason for early discontinuation/termination will be documented in the source documents and eCRFs.

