#### 2.2 **Overall Study Design and Plan**

This study is a prospective, randomized, multicenter clinical evaluation of the Edwards Cardioband System for the treatment of clinically significant functional mitral regurgitation in MR patients who are treated in accordance with current ACC/AHA valve guidelines. The study design incorporates a roll-in cohort to provide experience in use of the Edwards Cardioband System prior to randomizing patients into the pivotal study cohort at a given investigational site. The roll-in cohort will include a maximum of three patients per site (e.g. if 75 sites used, a maximum of 225 roll-in patients). Data for the roll-in patients will be presented and analyzed as a separate cohort. All patients are followed for 30 days, 6 months, 1 year, and annually for a total of five years post-index procedure or randomization in the case of the Control population.

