### 8.7 Long Term Outcomes (5 Years)

Descriptive statistics for long term outcomes will be compared between Device and Control groups.

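### Protocol 9 does not say whether Controls who cross over are still followed to 5 years from randomization; if the device is approved and only the two-year minimum is applied, they may have no year-4 and year-5 data

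*Protocol*

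**What the plan says.** Four places set a common 5-year follow-up:

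- Protocol 4 (Study Design): "long-term follow-up through 5 years is planned for all patients". For Controls the clock starts at randomization: "annually for a total of 5 years post-index procedure or randomization in the case of the control population".
- SAP 2.2 repeats the rule: "annually for a total of five years post-index procedure or randomization in the case of the Control population". SAP 2.4 also plans annual follow-up to 5 years for everyone.
- Protocol 12.2 says that all randomized patients "will be required to adhere to the assessment schedule outlined in Table 4". Table 4 runs to year 5, and 12.2 makes no exception for crossover.

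The crossover note in Protocol 9 is different. A Control may be offered the device "after they have been followed for a minimum of 1 year and completed their primary efficacy endpoint assessment". Crossing over takes both a choice and a new check: "if the patient chooses to receive the investigational device, they will be evaluated in accordance with the eligibility criteria", with agreement of the site Heart Team and the Central Screening Committee. An implanted Control is then followed on the "protocol schedule or at a minimum for two years if the product has received PMA Approval", and the group is summarized as a separate cohort. The note does not state the date from which the two years run, when approval must have been received, or whether the randomization-based visits continue.

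SAP 8.7 says: "Descriptive statistics for long term outcomes will be compared between Device and Control groups". SAP 3.9 lists those outcomes, including all-cause and cardiovascular death, HF hospitalization and transplantation. SAP 9.1 adds Kaplan-Meier estimates for death if the data suffice. The SAP has no rule for crossover patients.

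**The concern.** From these passages a site cannot tell whether a crossover patient still owes year-4 and year-5 data. The common rule says yes. The note in Protocol 9 can be read as permission to stop two years after implant once the device is approved. Supporting that approval is the stated purpose of the trial (Protocol 1 and 3), so the shorter option opens if the trial succeeds. The documents give patients randomized to Device no matching early stop.

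What is at stake is the long-term comparison by randomized arm. Crossovers must be alive at 1 year, want the device and meet the entry criteria again. Several of those criteria bear on prognosis, such as life expectancy, renal function and hemodynamic stability. If follow-up ends near year 3 for these patients only, the missing part of the Control arm is not a random part. Where they are tabulated can be changed at analysis; outcomes that were never collected cannot be recovered then.

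**Working it through.** **Visit windows.** SAP 5.2 gives year 4 as day 1400 to 1520 and year 5 as day 1765 to 1885. With 365 × year ± 60 days:

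- Year 4: 1460 ± 60 = 1400 to 1520, as printed.
- Year 5: 1825 ± 60 = 1765 to 1885, as printed.

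**End of follow-up under the two-year minimum.** The note does not date the two years; I count them from implant. End day = implant day + 730. Protocol 9 places the decision at the 1-year visit, whose window is day 320 to 410, and requires at least 1 year of follow-up first.

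- Implant at day 365: 365 + 730 = 1095, which is 1400 − 1095 = 305 days before the year-4 window opens.
- Implant at day 410: 410 + 730 = 1140, which is 1400 − 1140 = 260 days before.
- Even a two-year post-implant visit at the late end of its window, after a day-410 implant, falls at 410 + 730 + 60 = 1200.
- Year 4 is reached only with an implant on or after 1400 − 730 = day 670, and year 5 only on or after 1765 − 730 = day 1035.

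**End of follow-up under the full schedule.** A day-365 implant followed for 5 years ends at 365 + 1825 = day 2190, which covers years 4 and 5 from randomization. The gap therefore arises only under the minimum.

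**Number of patients.** Controls: 375/3 = 125. At the plan's 20% one-year mortality (Protocol 13.5), 125 × 0.80 = 100 are alive at 1 year. The documents give no crossover rate, so the rates below are assumptions, and each count supposes that every crossover patient stops at the minimum.

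| Assumed crossover | At most without years 4–5 | Controls left |
|---|---|---|
| 20% | 20 | 80 |
| 30% | 30 | 70 |
| 50% | 50 | 50 |

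**Loss of precision.** Device patients alive at 1 year: 250 × 0.80 = 200. For a difference in proportions near 50%, the 95% half-width is 1.96 × √(0.25/200 + 0.25/n), where n is the number of Controls left.

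- n = 100 (no loss): 12.0 points
- n = 80: 13.0 points
- n = 70: 13.6 points
- n = 50: 15.5 points

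These figures ignore deaths and dropout after year 1. The precision loss is modest. The larger worry is bias from selective loss, and the documents do not allow that to be calculated.

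**The case against.** A reader might infer that part of the Control arm will have no year-4 and year-5 outcomes. The documents do not support that. The same sentence in Protocol 9 also provides for the full schedule. A loss needs three things together: approval received, use of the minimum, and an implant before about day 670 (day 1035 for year 5). If approval follows the 1-year analysis, the earliest crossovers may already be past year 3 when the minimum becomes available. The 20 to 50 patients are therefore a ceiling on assumed rates, not an estimate.

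Nor would a 5-year as-randomized comparison be impossible. Crossovers would still contribute about three years, and SAP 5.1 censors survival analyses at the last information date, so a curve could be drawn. Its weakness would be censoring related to prognosis.

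The strongest counter-argument is that nothing cancels the duty in Protocol 12.2, and that Protocol 9 schedules visits by assigned group. On that reading the two years govern only the added post-implant visits. This is possible, but it is not stated, and a site could reasonably apply the minimum as the whole obligation.

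Two further objections stand in part. Once a Control is implanted, the long-term contrast is diluted, and moving crossovers to their own cohort leaves a selected Control group even with complete data. The early stop adds to those problems and is not their only cause. But the separate-cohort rule concerns reporting and cannot supply uncollected outcomes. The death-index check in Protocol 12.3 is written for patients lost to follow-up, and someone who completes a permitted minimum may not count as lost.

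**Conclusion.** The passages conflict or, at best, leave the duty unclear, and they need to be reconciled. If approval is received and only the two-year minimum is applied, Controls implanted near the 1-year visit may have no data for years 4 and 5 from randomization, and that loss would be selective. The timing rests on counting the two years from implant. The number affected is unknown, with an upper limit of 20 to 50 of about 100 one-year survivors at assumed crossover of 20% to 50%.

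This is a minor point. It touches only the descriptive long-term Device versus Control summaries in SAP 3.9, 8.7 and 9.1, which carry no test or success criterion. The 30-day safety endpoints concern the Device group only, and crossover is offered only after the 1-year efficacy assessment, so the co-primary, key secondary and 30-day safety results are not affected.

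**What to change.** - **Protocol 9:** state that every randomized Control, crossed over or not, is followed to 5 years from randomization, at least for vital status and HF hospitalization by telephone or record check. State that any two-year minimum applies only to the additional post-implant assessments, and give the date from which it runs. Bring this into line with Protocol 4 and 12.2 and SAP 2.2.
- **SAP 8.7 and 9.1:** state that an as-randomized long-term summary, with crossovers kept in Control, is presented alongside the separate crossover cohort.

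The cost is a wording change and a small amount of annual contact in years 4 and 5 for crossover patients. No extra clinic visit or procedure is needed. The change has to be in place before the first such patient exits.
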